4. STUDY OBJECTIVES

- To make treatment with laquinimod available to all subjects who previously participated in LAQ/5062 study and those who completed the Termination visit of LAQ/5063 active double-blind phase (completion of the full 36 weeks or as requested by the Sponsor).
- To assess the long-term safety, and tolerability in the group that received active treatment in LAQ/5062 protocol and additional short term safety and tolerability in the group who received placebo treatment. LAQ/5063 OL phase will assess long-term safety and tolerability of 0.6 mg laquinimod once daily.

Further efficacy data will be obtained by comparing baseline to termination in the group who received placebo treatment in LAQ/5062 core study protocol.

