4.1.2. Tolerability

- Number and percentage of subjects who prematurely discontinued from the study
- Number and percentage of subjects who prematurely discontinued from the study due to AEs

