7.1. Study Period

This is a continuation of the LAQ/5062 study as a multinational, multicenter, randomized, double-blind, parallel group study, assessing the safety, tolerability and efficacy of two doses of laquinimod in subjects with RRMS, followed by an open-label phase of laquinimod 0.6 mg daily (LAQ/5063 OL).

Subjects will enter this randomized, two active arms study immediately after completion of the LAQ/5062 core study. The blinding in both, core study (LAQ/5062) and its extension, will be maintained. Subjects will enter the open-label phase after completion of the Termination visit of LAQ/5063 active double-blind phase (completion of the full 36 weeks or as requested by the Sponsor).

The study duration is 36 weeks of double blind treatment (Week 0 [baseline] to Week 36 [termination]) or until the Sponsor's request. The duration of the open-label phase is as long as the Sponsor continues the development of laquinimod 0.6 mg for RRMS.

Subjects will be evaluated at study sites at Baseline (Week 0 / Termination (Week 36) of Core Study LAQ/5062), at Weeks 4, 8, 12, 16, 24, and 36 (Termination visit of LAQ/5063 active double-blind phase (completion of the full 36 weeks or as requested by the Sponsor).

For the Study 5063 open label extension phase, the visits will be at monthly intervals for the first 3 months and at three months intervals for the period of 24 months. Upon completion of the 24 month treatment period visits will be performed at 6 months intervals thereafter, where, for the purpose of this study, a month is 30 days and a visit is defined as X months \pm 7 days.

During the open label phase subjects will be evaluated at study sites for the following scheduled visits:

Baseline (Month 0 / Termination visit of LAQ/5063 active double-blind phase [completion of the full 36 weeks or as requested by the Sponsor]), Month 1, Month 2, Month 3, Month 6, Month 9, Month 12, Month 15, Month 18, Month 21, Month 24, Month 30, Month 36, Month 42, Month 48, Month 54, Month 60 and every 6 months thereafter, until termination (as long as the Sponsor continues the development of laquinimod 0.6 mg for RRMS) or early discontinuation.

Subjects who discontinue treatment for any reason will continue follow-up according to scheduled visits.

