7.3.3. Termination Visit

Termination Visit (6) / (Week 36 ± 3 days) of LAQ/5063 Active Double-Blind Phase (Completion of the full 36 weeks or as requested by the sponsor), or any Termination or Early Discontinuation visit occurring as long as the Sponsor continues the development of laquinimod 0.6 mg for RRMS.

In the event of early discontinuation, standard termination procedures will be followed.

Early discontinuation is defined as withdrawal from the study prior to the completion of the full study period:

- Withdrawal prior to completion of 24 months of the first period of open label phase.
- Subjects that chose to continue to the second period of open label phase (additional 36 months), and did not complete this period.
- Subjects that chose to continue treatment from Month 60 as long as the Sponsor continues the development of laquinimod 0.6 mg for RRMS and did not complete this period.

Subjects who are discontinued from study treatment will be encouraged to continue all scheduled visits and procedures until completion of the study (with the exception of procedures associated with drug dispensing and accountability, pregnancy testing, and GFR estimation [including body weight measurement]).

Subjects who have completed 24 months of open label phase and chose not to continue to further extension of open label phase will be regarded as completers.

Subjects who have completed 60 months of the extension open label phase and chose not to continue to further extension of open label phase (as long as the Sponsor continues the development of laquinimod 0.6 mg for RRMS) will be regarded as completers.

The reason for discontinuation of therapy will be documented in the source documents and captured on the CRF. If there are several reasons for early discontinuation, the more severe will be chosen as the primary reason. In the event that laquinimod is discontinued early, an early termination visit should be completed as close to the last dosing date as possible.

Subjects who did not complete the 36 weeks of treatment of LAQ/5063 active double-blind phase until approval of amendment No 2 will be called for an a termination visit of the active double-blind phase as requested by the Sponsor to be switched to the open-label phase (LAQ/5063 OL)

In case a subject completed the 60 months OL period, but decided not to proceed with the further extension, he/she will be considered as completer.

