7.3.4. Criteria for Early Termination

Subjects who are discontinued from study treatment will be encouraged to continue all scheduled visits and procedures until completion of the study (with the exception of procedures associated with drug dispensing and accountability, pregnancy testing, and GFR estimation [including body weight measurement]).

An early termination visit should be completed for all subjects who prematurely discontinue from the study and do not agree to or cannot continue all scheduled visits and procedures. It includes subjects who took at least one dose in the LAQ-5063 OL study.

Every attempt should be made to follow the early discontinued subjects. Subjects who prematurely discontinue the study should be followed and treated by the Site Investigator in a customary manner. For subjects who decide not to continue with any further visits, termination visit evaluations/procedures should be performed and completed before discontinuation. A subject may withdraw or be withdrawn from the study for the following reasons:

1. Subject withdrew consent (specify)
2. Teva requested that subject be withdrawn (specify)
3. Request of Investigator or Primary Care Physician (specify)
4. Non-compliance
5. Protocol violation
6. Loss to follow-up/failure to return
7. AE (specify primary AE)
8. Death
9. Pregnancy
10. Planned pregnancy
11. Lack of efficacy
12. Other (specify)

If a subject is withdrawn due to AEs, the appropriate AE sections of the CRF should be fully completed. The local clinical management (LCM)/Monitor should immediately be informed of any withdrawal. The primary AE that caused early discontinuation should be specified in the appropriate section in the CRF.

If an AE is present at the last visit, it will be followed until the medical condition returns to baseline or is considered stable or chronic.

All efforts should be made to follow a subject who prematurely discontinues the study due to ongoing AE. In case of manifestation of a severe degree of intolerance to IMP and/or ongoing exacerbation, the subject may be prematurely discontinued at the discretion of the Investigator.

Laboratory tests demonstrating clinically significant changes should be repeated and followed up until they return to normal or baseline levels, or are stabilized.

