11.5.5. Drug Tolerability & Drop-Out Assessment

The number and percentage of subjects who failed to complete the study will be presented by treatment groups.

The number and percentage of subjects who prematurely discontinued from the study due to AEs will be presented by treatment groups.

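### After Amendment 10 the tolerability outcomes still count exits from the study, so a drug stop for an adverse event in a subject who stays in follow-up is missed or counted inconsistently

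*Combined protocol and SAP*

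**What the plan says.** **Objective.** Section 4 states: "LAQ/5063 OL phase will assess long-term safety and tolerability of 0.6 mg laquinimod once daily".

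**Outcomes.** The synopsis and 4.1.2 list two tolerability measures: premature discontinuation from the study for any reason, and "Number and percentage of subjects who prematurely discontinued from the study due to AEs". Section 11.5.5 plans to tabulate subjects who fail to complete the study, and adds: "The number and percentage of subjects who prematurely discontinued from the study due to AEs will be presented by treatment groups". Section 7.3.3 fixes the meaning: "Early discontinuation is defined as withdrawal from the study prior to the completion of the full study period". No listed tolerability measure counts stopping the drug.

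**Follow-up after a drug stop.** Section 7.1 says: "Subjects who discontinue treatment for any reason will continue follow-up according to scheduled visits". The synopsis, 5.1 and 7.3.2 carry the same sentence, and Section 21.1 logs it as new text in Amendment 10. Sections 7.3.3 and 7.3.4 and the note to Table 7 are softer: these subjects are only encouraged to continue.

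**Early termination visit.** Section 7.3.3 says: "In the event that laquinimod is discontinued early, an early termination visit should be completed as close to the last dosing date as possible". Appendix 10 (items 1.1.3 and 1.2.1) likewise calls for early termination visit activities once a liver stopping rule is met. Section 7.3.4 instead asks for the visit from subjects "who prematurely discontinue from the study and do not agree to or cannot continue all scheduled visits and procedures".

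**Data collected.** Section 7.3.3 also says: "The reason for discontinuation of therapy will be documented in the source documents and captured on the CRF".

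**The concern.** Discontinuation due to AEs is one of only two tolerability measures, and long-term tolerability of 0.6 mg is a stated purpose of the open-label phase. The measure reflects drug intolerance only if stopping the drug and leaving the study happen together. Amendment 10 sets out to separate them, and for a good reason: more safety follow-up. Its log says that endpoints are not altered. The wording is indeed the same, but what that wording captures may not be.

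The better retention works, the fewer AE drug stops the declared outcome shows. Open-label subjects who stopped before and after Amendment 10 may also be counted on different bases. A reader of the final tolerability table could then take a low figure as good tolerability when part of it is good retention.

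**Working it through.** The plan gives no figure to reproduce, so the check is mainly one of wording.

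**Step 1. Trace a subject who permanently stops laquinimod for an AE in the open-label phase after Amendment 10.**

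| After the drug stop | Following 7.3.4 | Following 7.3.3 and Appendix 10 |
|---|---|---|
| Leaves the study | Early termination visit; counted | Early termination visit; counted |
| Stays in scheduled visits | No early termination visit; not counted | Early termination visit; counted only if the site records it as an exit |

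The first row is unambiguous. In the second row, the definition in 7.3.3 (withdrawal from the study) excludes the subject, but the visit rules allow two sites to record the same case differently.

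**Step 2. Express the shortfall.** Let k be the number of AE drug stops and r the share of them who stay and are not recorded as exits. The declared outcome shows k(1 − r), so the relative shortfall is r, whatever k is. Neither k nor r is in the documents. Assumed values of r:

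- r = 25%: 75% of AE drug stops shown
- r = 50%: 50% shown
- r = 90%: 10% shown

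**Step 3. Put it on the scale of the trial.** Section 21.1 gives 110 ongoing subjects at Amendment 10. Let p be the share of them who stop the drug for an AE, assumed to be 1% to 5%. The number uncounted is 110 × p × r:

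- lowest: 110 × 0.01 × 0.25 = 0.275, about 0.3 subjects, or 0.25 percentage points of 110
- highest: 110 × 0.05 × 0.90 = 4.95, about 5 subjects, or 4.5 percentage points of 110

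Each uncounted subject is 100/110 = 0.91 percentage points of those ongoing, or 100/264 = 0.38 percentage points of the maximum cohort of 264 given in Section 11.

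**Step 4. Check whether another table carries the number.** Section 11.5.1 tabulates AEs by maximal action taken, which partly does so. Two gaps remain. First, the protocol lists no action categories, and 7.3.5 allows temporary interruption for an intolerable AE, so permanent stops may not be separable. Second, Section 10 treats an abnormal laboratory result as an AE only under listed conditions: withdrawal of the subject by the investigator, association with a serious AE, clinical signs or symptoms, or clinical significance in the physician's view. A retained subject stopped on an asymptomatic laboratory threshold may therefore reach the AE tables only through the last of these.

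**Step 5. Apply the fix.** A count of permanent drug discontinuation due to AEs reports k, whatever r is.

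**The case against.** **Section 11 was written for another phase.** It describes 36 weeks of double-blind treatment, its MRI endpoints are at Week 36, and 11.5.5 reports by treatment group. The open-label phase gets one line, on dosing, in 11.2. This stands in part: 11.5.5 alone is a weak anchor. But the outcome lists in the synopsis and 4.1.2 are not limited to the double-blind phase, and Section 4 sets open-label tolerability as an aim. If 11.5.5 does not apply there, that aim has no stated tolerability analysis.

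**The protocol uses discontinuation loosely.** Under 7.3.3, the category for Month 60 onward refers to subjects who chose to continue treatment and did not complete the period, which can be read as keyed to the drug. This also stands in part. It turns a certain omission into an ambiguous count, but it does not supply a measure of drug discontinuation.

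**The information is collected.** The CRF holds the reason for stopping therapy, and AE tables by action taken exist. This stands, and it is why the fix is cheap. It does not change what the declared outcome reports.

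**Stronger readings that the documents do not support.** A reader might infer that every AE drug stop drops out of the count. Retention is only encouraged in 7.3.3 and 7.3.4, so some subjects will leave and be counted. A reader might also infer that a stop under a liver rule can never be recorded as an early termination. Appendix 10 requires early termination visit activities in those cases and sets a minimum follow-up after early termination, so it can be. Finally, the exit of pregnant subjects in Appendix 10 item 7 might look like a further contradiction. Section 7.3.4 lists pregnancy as a reason for withdrawal, so this appears to be a deliberate exception, and it has no bearing on tolerability.

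**Conclusion.** The concern holds in limited form. For the open-label phase after Amendment 10, a subject who stops laquinimod for an AE and stays in follow-up is either outside the tolerability outcome on its literal wording or counted according to how the site reads conflicting visit rules. The likely direction is to understate drug intolerance.

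The size cannot be computed from the documents. The range of 0.3 to 5 subjects rests wholly on assumed stop rates of 1% to 5% and assumed shares of 25% to 90%; the upper share in particular has no support in the text. Few subjects are affected. The analyses are descriptive, so no error rate or power is involved. The double-blind comparison of 0.3 mg and 0.6 mg is untouched: under 7.3.3, subjects still in that phase were called to a termination visit at Amendment 2, well before the retention rule.

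The change should be made because the outcome serves a stated objective and the correction needs no new data. It is not a threat to the validity of the trial.

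**What to change.** 1. In the synopsis, 4.1.2 and 11.5.5, report the number and percentage who permanently discontinue study drug, overall and due to AEs, separately from the number and percentage who withdraw from the study, overall and due to AEs. State that this applies to the open-label phase. Take the reason from the CRF field for stopping therapy.
2. In 7.3.3 and Appendix 10, state that an early termination visit after a drug stop does not end scheduled follow-up and is not in itself a study withdrawal. Align 7.3.4 with this.

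The cost is one extra descriptive table from data already collected, plus wording in those sections. No new visit, procedure or CRF item is needed.

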12. REGULATORY AND ETHICAL ISSUES

12.1. Compliance With Regulations Applicable To Clinical Trials

The study will be conducted according to the laws, regulations and administrative provisions relating to the implementation of GCP in the conduct of clinical trials on medicinal products for human use, as applicable by national legislation and directives, including Directive 2001/20/EC of the European Parliament and the Council of the EU.

12.2. Informed Consent

The principles of Informed Consent, according to the ICH step 5 guidelines on GCP, and/or EU Directives, will be followed. A subject should not enter a clinical study or perform any study-related procedures until he/she has been properly informed, has been given time to contemplate participation, and has freely given his/her consent by signing and dating the EC approved informed consent form.

A signed copy of the consent form will be given to the subject and the original will be maintained at the site following the signing and dating by the person administering the consent and witness (where appropriate).

A copy of the proposed consent form must be submitted to the EC, together with the protocol, and approved prior to study start.

Subjects continuing on laquinimod 0.6 mg will be re-consented with information about the cardiovascular risk seen in higher doses (see Section 3.4.1.7).

12.3. Ethics Committee

The EC has to issue a favorable opinion in order to allow the start of the clinical trial. Teva must receive, prior to site initiation, a copy of the written EC opinion which contains specific identification of the documents approved.

Any substantial^m amendments to the protocol or subsequent changes to the informed consent form as a result of changes to the protocol and/or IB that is approved by Teva, must also be sent to the EC and written opinion has to be provided to Teva. Records of the EC review and opinion of all documents pertaining to this study must be kept on file by the Investigator and are subject to regulatory authority and/or Sponsor inspection during or after completion of the study. SAEs must be reported to the EC by the Sponsor.

^m as defined in the EU in the “Detailed guidance for the request for authorization of a clinical trial on a medicinal product for human use to the competent authorities, notification of substantial amendments and declaration of the end of the trial” (ENTR/CT April 2004)

Periodic status reports must be submitted to the EC as required, as well as notification of completion of the study and a final report where applicable. A copy of all reports submitted to the EC must be sent to the Sponsor.

12.4. Protocol Amendments

For clinical trial sites located in EU member states, the procedures outlined in Directive 2001/20/EC, Article 10(a), are applicable. Elsewhere, the country regulations apply.

12.5. Declaration Of The End Of The Clinical Trial

For clinical trial sites located in EU member states, a declaration of the end of the clinical trial will be made according to the procedures outlined in Directive 2001/20/EC, Article 10(c). Elsewhere, the country regulations apply.

12.6. Subject Confidentiality

The Sponsor is concerned about the individual subject's privacy; therefore, all subject data will be identified by a subject identification number. The data will be blinded correspondingly in all data analyses. However, after receiving the subject's approval (by signing the Informed Consent), it is required that the Investigator permit the Study Monitor, independent auditor or regulatory agency personnel (with or without the Investigator) to review that portion of the subject's medical record that is directly related to the study. This shall include all study relevant documentation including subject medical history to verify eligibility; laboratory test result reports; admission/ discharge summaries for hospital admissions occurring while the subject is in the study; and autopsy reports for deaths occurring during the study (where applicable).

The subject's authorization allows Teva to receive and review the subject's protected health information which may be re-disclosed to any authorized representative of Teva or central laboratory facility for review of subject medical records in the context of the study.

12.7. Liability And Insurance

A Certificate of Clinical Trials Insurance will be provided to the study sites by Teva Pharmaceutical Industries, Ltd in addition to the local certificate, as per local regulations.

13. DOCUMENTATION

13.1. Study File And Site Documents

Prior to the initiation of the study, the following documents must be provided to Teva Pharmaceutical Industries, Ltd.:

1. Confidentiality Agreement signed by Principal Site Investigator (PSI)
2. Copy of the protocol, amendments and notifications (if applicable), signed by the PSI
3. The PSI's curriculum vitae
4. Signed Clinical Study Agreement with site
5. EC written opinion for the protocol, amendments, informed consent, subject information sheet (if applicable), advertisements (if applicable) and membership list
6. CA written opinion (if applicable)
7. Hospital Management opinion (if applicable)
8. PSI's financial disclosure information

13.2. Site Documents/Equipment Supplied By The Sponsor

Prior to the initiation of the study, the Sponsor will supply the Site Investigator with the following items, in addition to the protocol:

- Current version of the IB
- Central Laboratory certification and normal range values
- Portable Computer for Data Capturing (including Oracle Clinical Remote Data Capture [RDC[®]] application; see Section 13.4)
- A hard copy of the electronic CRF in PDF format
- User Manual for the RDC[®]
- Regulatory Binder
- Informed Consent Template
- Insurance Certificate

- Subjects study binder, including source pages to be used during the study if hospital clinic office records are not used.

13.3. Maintenance And Retention Of Records

It is the responsibility of the Site Investigator to maintain a comprehensive and centralized filing system of all relevant documentation.

Site Investigators will be instructed to retain all study records required by Teva and regulatory authorities in a secure and safe facility with limited access for one of the following time periods based on notification from Teva:

- at least 2 years from the last marketing approval worldwide, or for at least 15 years, whichever is the greater; or
- longer if required by local regulations

The Site Investigator will be instructed to consult with Teva before disposal of any study records and to notify Teva of any change in the location, disposition or custody of the study files.

At the end of the study, the sponsor will supply the site investigator a copy of the site's subjects electronic CRF in PDF format.

